5.4 PARTICIPANT RECRUITMENT

Returning a mailed baseline survey will enroll a potential participant in the study. We will use a modified Dillman protocol to maximize recruitment response rates and data quality.¹⁰ First, we will send each patient a letter from the Chief of Staff and facility Behavioral Health Coordinator (or other comparable leader from the facility) stating they will soon be contacted about a smoking cessation research study with the goal of helping Veterans who use VA mental health clinics stop smoking (Appendix A). The letter will also include information on how to contact the project director to opt out of receiving further study materials (flyer and baseline survey described below) or if they feel they have been contacted in error (e.g., not a current smoker). One week later, we will send out a packet of information, including a cover letter (Appendix B), a sheet of Frequently Asked Questions (FAQ; Appendix C), and the self-administered baseline survey. The cover letter and FAQ sheet accompanying the mailed baseline survey will contain all the elements of informed consent and explain the purpose of the study. Patients will have information that will explain the study's risk and benefits, that names are not attached to study documents and that choosing to participate or not to participate in the study will have no effect on their medical care. They will also be informed that they will receive a \$10 payment for returning the survey. These documents will contain telephone numbers if participants have further questions about the study. Potential participants can also contact us if they wished to be no longer contacted by the study.

5.5 RANDOMIZATION AND BLINDING

After returning the baseline survey, we will randomize respondents in a 1:1 fashion to intervention or control, stratified by site. To randomize a patient, the Project Director will log onto the study's database system (which will be adapted from the one used in [name] previous studies), enter the subject's unique study ID, confirm eligibility, and confirm that the survey has been received. The database system verifies that all randomization criteria have been satisfied, then assigns a study ID and a group to the subject. The database system will automatically input the date of randomization and the participant's assignment into their study record. The study's Project Director and counselors will have access to treatment assignments. The study's research assistants and our biochemical validation company (Salimetrics, described in section 4.0) will be kept blind to treatment assignments. Intervention participants will be aware of the arm to which they are assigned when they receive the first phone call from a study counselor.

5.6 STUDY GROUPS

INTERVENTION

Telephone Counseling

Within one week of receiving a completed baseline survey, a counselor will phone intervention participants. Up to 6 contact attempts will be made at different times (i.e., morning, afternoon, evening) during the week. The purpose of the outreach call is to: 1) deliver motivational enhancement to quit smoking, 2) promote self-efficacy, and 3) encourage participants to participate in smoking cessation treatment. The full telephone counseling protocol is characterized by:

- *Motivational enhancement* – We will include motivational enhancement in each of the first several telephone calls and as-needed during later calls to increase patient motivation to quit and reduce relapse.

- ❑ *Multiple sessions* – Participating smokers will receive 8 calls over two months and then, for those who quit in this timeframe, monthly maintenance calls for six months. The initial call will be 30-45 minutes and subsequent calls will be 10-20 minutes.
- ❑ *Relapse-sensitive scheduling* – Participants will receive 4 calls to plan a quit date, three calls in the first two weeks after their Quit Date, when the relapse risk is highest, followed by another call in another two weeks. Patients who are quit at the 8 week call will receive monthly maintenance calls to work through any slips or barriers to continued abstinence.^{11,12}
- ❑ *Problem-solving therapy* – This approach, based on helping the smoker identify and solve expected and actual challenge, is endorsed by the national smoking cessation guidelines.¹³
- ❑ *Stress Reduction* – Our previous work providing tobacco cessation counseling to VA mental health patients identified stress and anxiety as a major barrier toward quitting and long-term abstinence among this population. Our counseling protocol includes stress reduction techniques, such as relaxation and mindfulness exercises,^{11,12} and the incorporation of smoking schedules to remove the link between smoking and stress responses.¹⁴ We will also send stress reduction self-help materials to intervention participants that the counselors will discuss during the counseling.

Medication Requests

All smokers in the intervention arm will be asked about their NRT preference during their first counseling call. Their counselor will place a View Alert in CPRS for their facility's smoking cessation program or regular primary care provider indicating that the participant expressed interest in receiving NRT and their preference. The View Alert will also contain relevant information from the US Public Health Services guidelines for the treatment of tobacco. The counselors will monitor the participants' EMR for whether a prescription is written. If no prescription is written within 1 week after sending the View Alert, the counselor will place a follow-up View Alert reiterating the participant's expressed interest in NRT. The regular smoking cessation providers will not be required to prescribe or be required to prescribe the patient's preferred NRT. Rather, study staff will simply notify the providers that the patient expressed interest in receiving NRT. The Intervention counselors will also encourage participants to discuss NRT use with their regular providers.

Engaging MH Providers in the Treatment Process

In recognizing that a patient's regular Mental Health providers are an important source of support and treatment encouragement for our patient population, we will engage all intervention patients' primary mental health providers into the treatment process by alerting the providers of their patients' progress via CPRS progress notes and providing them information via email about the program and how they can support their patients. As we have done with [name] prior studies, the study's counselors will place a progress note into CPRS for each patient documenting the first counseling call and the quit plan developed during that call. Additional progress notes will be entered into the medical record when the patient quits smoking, when there is a significant change in the quit plan, and when the patient is discharged from the program. On each note, the patient's primary Mental Health provider (identified on the baseline survey and confirmed with EMR review) and psychiatrist (if different from the primary provider) will be added as an additional signer to the note. This process will also ensure the safety of participants using antipsychotic medications by notifying their psychiatrist of their quitting process.

CONTROL GROUP (USUAL VA CARE)

We will send smokers randomized to the control group a mailed list of local VA and non-VA smoking cessation services that they can access on their own. In addition, patients randomized to the control group may receive treatment or referrals to treatment from their regular VA providers as part of usual care. Pharmacotherapy is available at all sites in the form of nicotine replacement (patches, gum and lozenges) and bupropion.

5.7 DATA COLLECTION

All participants will be surveyed by mail at baseline, by mail 2 weeks after enrollment, and by telephone (or mail for non-respondents) at 6 and 12 months from enrollment. Research assistants will make up to 10 attempts at different days and times to reach participants by phone for the 6 and 12 month surveys. If we cannot reach a participant after 10 attempts, we will mail a paper version of the survey with a cover letter (Appendix K) to participants. Patients will receive a \$10 payment as reimbursement for completing each survey.

5.7.1 Baseline Survey

Smoking questions

- Smoking habits and history.* We will use measures adapted from the California Tobacco Survey¹⁵ that we have used in several previous studies to assess the number of cigarettes smoked per day, number of days smoking per week, and nicotine dependence..¹⁶
- Motivation.* We will assess readiness for change using the Stage of Change scale.¹⁷
- Tobacco treatment used in prior 12 months.* We will ask participants to indicate whether a VA provider talked to them about smoking in the prior 12 months and which tobacco treatments they used in the prior 12 months.
- Health.* We will ask a single item asking participants to rate their general level of health on a 5-point Likert type scale.

5.7.2 2-Week Survey

Sociodemographics

- Demographics.* Age, sex, marital/partnership status, race/ethnicity, education, and occupation will be assessed, as well as text messaging interest and capabilities.
- Environment.* Using questions from the California Tobacco Survey¹⁵ we will assess household tobacco use and restrictions on smoking at home.

Smoking questions

- Smoking habits and history.* We will use measures adapted from the California Tobacco Survey¹⁵ that we have used in several previous studies.
- Self-Efficacy.* Self-efficacy for smoking cessation will be measured with the 14-item Confidence Questionnaire Form¹⁸ which assesses smoking cessation self-efficacy across 14 different situations or mood states.
- Pros and Cons.* We will use the 6-item decisional balance scale which measures positive and negative attitudes toward quitting.¹⁹
- Perceptions regarding tobacco use.* We will also assess perceived control over withdrawal symptoms⁷⁴ and perceived antismoking norms,²⁰⁻²⁴ measures that predict tobacco use.

Health questions

- ❑ *Health habits.* We will use the AUDIT-C^{24,25} to assess alcohol use and a single item measure developed to assess drug use in primary care.²⁶ We will measure frequency, type and quantity of exercise using questions from the National Health Interview Survey.
- ❑ *Comorbidities.* We will assess baseline comorbid conditions using the survey version of the Charlson index.²⁷
- ❑ *Mental Health.* We will use the Kessler-6 psychological distress scale, as used by the National Survey on Drug Use and Health to measure general psychological distress.²⁸ The scale validity discriminates between cases and non-cases of mental illness. In addition we will use 14-item Hospital Anxiety and Depression Scale²⁹ to assess specific mood symptoms.
- ❑ *Mental Health provider.* In order to coordinate care and encourage involvement of the mental health clinicians, we will ask each patient for the name of the person he/she identifies as his/her primary mental health provider. This would be the provider he/she sees the most or feels is the most involved in his/her mental health care.

5.7.3 6- and 12-Month Surveys

All measures assessed at baseline and 2 weeks (except the sociodemographic measures) will be assessed again at 6 and 12 months. In addition, we will assess:

- ❑ *Cessation outcomes at 6 and 12 months:* We will follow recommended guidelines for measuring and validating tobacco abstinence in clinical trials.^{30,31} Smoking cessation (7-day point prevalence), quit attempts, reduction in smoking, use of cessation pharmacotherapy, and counseling received outside of this study will be collected.

5.7.4 Saliva Sample - Validation of self-reported abstinence

Self-reported smoking abstinence can be verified by assays of cotinine, the principal metabolite of nicotine. Patients with cotinine levels > 15ng/ml will be classified as current smokers.³² Sample collection will be conducted by mail. Patients will be eligible for verification if they report 7-day abstinence from cigarettes, other tobacco products, e-cigarettes and nicotine replacement therapy (NRT). A research assistant will send a saliva collection kit, collection instructions (Appendix D), a collection date sheet (Appendix E), and a postage-paid return envelope on the day of telephone survey with a postage paid return envelope. Subjects will receive a reminder call 5 and 8 days later. If they do not respond, another kit will be sent at 2 weeks, followed by two more reminder calls. We will mail a \$25 payment to participants who return a saliva sample.

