5.8 OUTCOMES

The primary outcome will be cotinine-validated abstinence from smoking at 12-month follow-up. Secondary outcomes include the following:

1. Self-reported 7-day abstinence (to estimate rates of misreporting) at 6 and 12 month follow-up.
2. Other cessation related outcomes at 6 and 12 months – e.g., quit attempts, cigarettes per day, cessation medication use, motivation, and self-efficacy.
3. Self-reported mental health distress and active substance abuse.

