We anticipate low, but potentially important rates of survey non-response to all or part of the 6- and 12-month surveys. We will use the evidence-based recruitment strategies described above (incentives, reminders, mixed mode survey administration) to minimize non-response. A common practice in smoking cessation research is to treat non-respondents at follow-up as continuing smokers (i.e., intent to treat). This practice is perceived to be a conservative approach but does not, in fact, produce valid estimates of quit rates.³³ We will use multiple imputations to fully use available baseline information and partial later surveys. We will use a propensity-based multiple imputation method similar to that discussed by Little³⁴ using separate imputation procedures within each study group and design stratum combination. Within a given combination, we will estimate the propensity for responding to cotinine validated abstinence for each individual from a logistic regression model for survey response using the characteristics measured at baseline as explanatory measures. Within a combination of intervention and design strata, we will further stratify the sample according to the values for these estimated propensities. Within a propensity substratum, we will impute a value for the outcome measure for each non-respondent by randomly sampling an outcome value from the respondent values in the substratum. Multiple completed datasets will be created and the point estimates and the estimated standard error from each dataset will be combined to arrive at a single point estimate (using the specific method discussed below), its estimated standard error, and the associated confidence interval or significance test. This approach assumes that missing outcome data due to non-response is missing at random.

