To assess the impact of non-ignorable survey non-response, or missing not at random non-response, we will implement pattern-mixture analyses. Using content expertise and the observed missing data patterns, we will develop these pattern-mixture models. The nature of these models is difficult to specify in advance of observing the different patterns but we will posit distributions for the missing data. For each set of posited distributions and the observed data, we will calculate revised estimates for the relevant intervention effects. One potential model would be to use the propensity stratum derived in the analysis described above and, within each stratum build a distribution for the outcome of interest by shifting the observed distribution among the responders. Content expertise and empirical results will be used to determine the form and magnitude of shift. These distributions would then be used to impute values for the non-responders to cotinine validation in the imputation process described immediately above. Variations of this approach and other approaches will be used to assess the sensitivity of the analyses above to non-ignorable non-response.

We will be enrolling patients after they complete the baseline survey, which maximizes our internal validity; thus we will have baseline data on all participants. The methods above for imputing missing data address the issue of non-response to all or part of either the 6-month or 12-month survey and cotinine validation. We will have limited data available on those who do not respond to the baseline survey, but we will use what data we have to compare initial responders to non-responders, in order to address external validity.

Specific aim analysis

The data will first be summarized numerically using descriptive statistics and frequency distributions examined for validity. Comparison of the baseline demographic and tobacco use characteristics between the two treatment groups will be performed using chi-square tests for categorical data and t-tests or nonparametric tests for ordinal or continuous data.

Aim 1: Compare the reach and efficacy of a proactive outreach telephone-based tobacco cessation (PRO) program for patients seen in mental health to usual care (UC) advice and referral to local VA and community tobacco cessation resources.

H1: Compared to the control group, the proactive intervention will increase the smoking abstinence rate at 12 month follow up.

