Method: The study design is a randomized block design with the blocks comprising combinations of the four hospital sites.

We will address the question of Reach via two indices:

- Proportion of patients who respond to the outreach letters and enroll in the study (i.e., completed the baseline survey). This analysis will help us understand the proportion of smokers in Mental Health who will respond to proactive outreach. Given the innovative nature of the proactive outreach approach, we will examine the acceptability of the intervention to determine which patients are more likely to accept treatment in the PRO and UC conditions. Specifically, we will use multivariable logistic regression to determine which baseline characteristics (e.g., age, race/ethnicity, income, mental health diagnosis, symptom severity) are associated with receipt of cessation counseling (state quitline or VA) or use of cessation medications.
- Proportion of patients who engage in at least one treatment session compared to control patients. Specifically, we will determine how many patients in the intervention arm used treatment (counseling and/or medications) and compare this to the number of patients

enrolled in the control arm who report using existing VA tobacco cessation services on the follow-up surveys, which will provide data regarding acceptability of treatment.

The primary smoking outcome variable that is expected to be affected by treatment is dichotomous cotinine-validated abstinence at 12 months post-enrollment. The comparisons of the abstinence rates across the two groups will be made using exact logistic regression methods, accounting for stratification by site, to model the log odds of use of smoking cessation treatment and log odds of 12-month abstinence. Exact logistic regression employs the non-parametric Chi-square test or Fisher's exact test.³⁵ These tests are widely applicable in complete randomized experimental designs that yield contingency tables. Fisher's exact test is particularly suitable for contingency tables with small and unbalanced frequency counts, which are to be expected for the population-based outcome we have chosen where our population quit rate in the control condition is expected to be 4%.

Aim 2: Model longitudinal associations between baseline sociodemographic, medical and mental health characteristics and validated abstinence at 6 and 12 months in the PRO and UC conditions.

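### The written imputation steps ignore the 12-month self-report, so a self-reported quitter without a cotinine result would be imputed a smoker about 94–96% of the time

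*Combined protocol and SAP*

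**What the plan says.** Section 5.8 defines the endpoint: "The primary outcome will be cotinine-validated abstinence from smoking at 12-month follow-up". The Aim 1 analysis in section 6.0 uses the same variable, "dichotomous cotinine-validated abstinence at 12 months post-enrollment".

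Section 5.7.4 limits who is tested: "Patients will be eligible for verification if they report 7-day abstinence from cigarettes, other tobacco products, e-cigarettes and nicotine replacement therapy (NRT". Its only classification rule, a cotinine level above 15 ng/ml, needs a sample. Kits are mailed, with reminder calls and a second kit, so some will not come back.

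Section 6.0, Missing Data, states a broad aim: "We will use multiple imputations to fully use available baseline information and partial later surveys". It says that counting non-respondents as smokers "does not, in fact, produce valid estimates of quit rates". The procedure works separately within each arm and design stratum. It estimates a response propensity from a "logistic regression model for survey response using the characteristics measured at baseline as explanatory measures", forms substrata on that propensity, and imputes "by randomly sampling an outcome value from the respondent values in the substratum". The section later says these methods "address the issue of non-response to all or part of either the 6-month or 12-month survey and cotinine validation".

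Section 5.7.3 collects 7-day point-prevalence abstinence and use of cessation medication at 12 months.

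**The concern.** Among people who answer the 12-month survey, a cotinine result can be missing only for those who report abstinence, because nobody else is sent a kit. Missingness of validation therefore depends on the 12-month self-report. The plan assumes data are missing at random. For these people that is credible only if the imputation conditions on the self-report, and the written steps do not.

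Instead, a self-reported quitter with no result is matched on baseline characteristics to people who mostly still smoke, and takes one of their outcomes. Both arms' abstinence rates are pulled down, and so is the difference between them. The missing-data section argues against this outcome but nearly reproduces it for the people whose 12-month status is best documented.

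A related gap is the NRT or e-cigarette user who has stopped smoking. Withholding the kit is reasonable, since nicotine from these products could raise cotinine. The plan does not say whether that person is a cotinine non-responder, to be imputed, or simply not validated.

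**Working it through.** **Planned figures.** Section 6.0, Power calculations, gives 1,920 per arm, 4% in UC, and 20% of PRO accepting counseling with a 16% quit rate. PRO rate: 0.20 × 16% + 0.80 × 4% = 6.4%. A two-sided 0.05 pooled two-proportion test gives power 91.8%, against the stated 90%. The planning figures reproduce.

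**Chance of being imputed a smoker.** If donors are all respondents in the cell, self-reported smokers included, and cells have on average the planned rates:

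- UC: 1 − 0.04 = 96.0%
- PRO: 1 − 0.064 = 93.6%

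**Effect of unreturned kits (illustration).** Let *p* be the validated rate if every kit came back (4% or 6.4%), *c* the share of tested quitters confirmed, and *r* the share of kits returned. The documents give neither *c* nor *r*. I assume *c* = 70–90% and *r* = 60–80%, equal in both arms, with full survey response and no kit-ineligible quitters.

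- Self-reported quitters: *p*/*c*
- Missing a result: *m* = (*p*/*c*)(1 − *r*)
- As-written estimate: *pr*/(1 − *m*)
- Missing = smoking: *pr*
- Conditioned on self-report: *pr* + *mc* = *p*

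Example, *r* = 0.6 and *c* = 0.7. UC: *m* = 0.0571 × 0.4 = 0.0229, estimate 0.024/0.9771 = 2.46%. PRO: *m* = 0.0914 × 0.4 = 0.0366, estimate 0.0384/0.9634 = 3.99%. Difference 1.53 points.

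| *r* | *c* | UC as written | PRO as written | Difference (points) | Difference if missing = smoking |
|---|---|---|---|---|---|
| 0.6 | 0.7 | 2.46% | 3.99% | 1.53 | 1.44 |
| 0.6 | 0.9 | 2.44% | 3.95% | 1.51 | 1.44 |
| 0.8 | 0.7 | 3.24% | 5.22% | 1.98 | 1.92 |
| 0.8 | 0.9 | 3.23% | 5.19% | 1.97 | 1.92 |

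The as-written difference is within 0.1 point of the missing = smoking result in every row. Conditioning on self-report returns 4.0% and 6.4%, a 2.4-point difference, if untested quitters would be confirmed at the same rate as tested ones. I give no power for the as-written case, because the multiple-imputation variance was not modelled.

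**Donor numbers for the fix.** With 1,920/4 = 480 per arm per site, if sites enroll equally, tested quitters number 480 × (*p*/*c*) × *r*. UC: from 480 × 0.0444 × 0.6 = 12.8 to 480 × 0.0571 × 0.8 = 21.9. PRO: from 480 × 0.0711 × 0.6 = 20.5 to 480 × 0.0914 × 0.8 = 35.1. This is before survey loss and before any split by propensity, so pooling would be needed.

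**The case against.** **The stated aim already covers this.** The aim to use partial later surveys could be read as a promise to use the 12-month self-report. It shows the intent, but none of the steps that follow carries it out.

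**Donors might be tested quitters only.** The text does not define respondents. But one procedure serves every non-respondent. With only tested quitters as donors, people who never answered the survey would also be imputed mostly abstinent, which cannot be squared with a planned 4% control rate. The broader donor pool is much the likelier reading.

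**Other analyses use the self-report.** Self-reported 7-day abstinence is a secondary outcome, and pattern-mixture analyses are planned for cotinine non-responders. Both reduce the consequence. Neither repairs the primary estimate, and the form and size of the pattern-mixture shift are left open.

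**Kit-ineligible users may be covered or may be few.** Someone without a cotinine result fits the wording about non-response to validation reasonably well, and section 5.7.3 commits to published validation guidelines. Scoring such people as not validated would also be defensible. This stands: on its own, the unstated score is a missing detail.

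**A tempting stronger reading** is that PRO, by forwarding NRT preferences to prescribers, loses more quitters to the kit rule and so biases the trial against itself. The documents do not support that. Counseling calls end at about 8 months (two months plus six monthly calls), UC patients also have access to NRT, and no month-12 use figure is given for either arm.

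**Conclusion.** The fault lies in the written imputation procedure. It does not use the 12-month self-report, so under the likely donor pool a self-reported quitter without a cotinine result is imputed a smoker about 96% (UC) or 94% (PRO) of the time. Under the assumed kit return and confirmation rates, the planned 2.4-point difference becomes about 1.5–2.0 points. That range also assumes that 4% and 6.4% are the rates with every kit returned and that return is equal across arms. If the planned rates already allow for lost kits, the power statement is unaffected, but the estimate would still be pulled towards missing = smoking.

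For NRT and e-cigarette users, only the absence of a scoring rule is established. A reader might infer a large loss of power or a bias of known direction from that group. Either would rest on month-12 use rates that the plan does not contain.

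**What to change.** In section 6.0, Missing Data:

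1. Score participants who report smoking at 12 months directly as not abstinent.
2. For self-reported quitters with no cotinine result, condition the imputation on 12-month self-reported abstinence within arm. Use as donors the self-reported quitters who have a result, and pool sites or propensity strata where that cell is small.
3. Impute survey non-respondents as now planned.

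In sections 5.7.4 and 5.8, keep the kit rule and state how self-reported quitters who get no kit because of NRT or e-cigarette use are scored. Report their number by arm. Bound the primary result by counting all of them as abstinent and then all as not abstinent. Settle this before outcome data are seen by arm.

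The cost is about a paragraph of text and one more conditioning variable. No new assay or survey item is needed, since kit eligibility already depends on these answers. The drawback is that imputed successes are unverified and assume untested quitters misreport at the same rate as tested ones. The planned pattern-mixture analysis can vary that assumption.
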